4.5.2 Benefits associated with Eltrombopag use

Eltrombopag is an oral TPO-RA approved in over 100 countries for the treatment of patients aged 1 year and above with primary ITP lasting 6 months or longer from diagnosis and who are refractory to other treatments. It has a well-established efficacy and safety profile with evidence of improved QoL responses in addition to improvement in platelet counts.

Eltrombopag has been shown to be superior to placebo in raising and maintaining platelet count above 50×10^9 /L for 6 months with a significant reduction in bleeding symptoms in previously treated chronic ITP patients. Eltrombopag also enabled more subjects to reduce/discontinue concomitant (corticosteroid) medication use (RAISE Study) (Cheng et al 2011).

Patients with severe "acute" and persistent ITP showed benefit from eltrombopag therapy initiated within 6 months from diagnosis. This was demonstrated in a multicenter, single arm open label study of 39 patients (platelet count $< 30 \times 10^{9}$ /L despite being dosed with 1 mg/kg prednisone for at least 2 weeks from diagnosis or requiring prednisone $\geq 10 \text{ mg QD}$ and/or recurrent doses of IVIg to maintain a platelet count of $\geq 30 \times 10^{9}$ /L within 6 months of diagnosis). Patients with platelets $< 10 \times 10^{9}$ //L began eltrombopag 75 mg QD while those with a count $\geq 10 \times 10^{9}$ /L began treatment with 50 mg QD. The eltrombopag dose was increased by 25 mg every 2 weeks to a maximum of 150 mg QD if the platelet count remained $\leq 30 \times 10^{9}/L$ or there was clinically significant bleeding every 2 weeks. The steroid could be decreased to zero over the subsequent 6 weeks if clinically appropriate. The primary endpoint was overall response rate (ORR) at week 12, defined as the proportion of patients achieving CR (platelet count > $100 \times 10^{9}/L$), partial response (PR) (platelet count > $50 \times 10^{9}/L$) or minor response (MR) (platelet $\ge 30 \times 10^{9}$ /L with $\ge 50\%$ reduction in the dose intensity of concomitant ITP therapy compared with screening). At Week 12, the ORR was 64%; at Week 26, the ORR was 54%. Two patients had serious adverse events (SAEs) with two episodes of venous thromboembolism (one deep vein thrombosis at platelet count 97×10^{9} /L; one pulmonary embolism at platelet count 240×10^{9} /L). There were no other AEs or deaths (Tran et al 2017).

In addition to the benefits described above, a possible direct immunomodulatory effect of eltrombopag has been postulated from small retrospective reviews. TPO-RA have been shown to dampen immune responses in chronic ITP by increasing the levels of anti-inflammatory cytokines and by reducing the levels of pro-inflammatory cytokines, increasing the suppressive activity of regulatory T-cells and reducing phagocytic activity of monocytes and macrophages, via modulation of Fc γ receptors towards inhibitory phenotype (Bao et al 2010, Qu et al 2017, Liu et al 2016).

There is also evidence that a proportion of patients go into remission and no longer require treatment after a number of months of eltrombopag therapy. This action of eltrombopag on ITP may be the result of a direct immunomodulatory effect that could impact other diseases as well (see Section 1.1.3).

5 Population

The study is designed to include 106 adult patients with newly diagnosed primary ITP with screening platelet count $< 30 \times 10^{9}$ /L and assessed as required treatment (per physician's discretion).

ITP patients are detected by routine examinations or in the context of preoperative clarifications. If a diagnosis of ITP is confirmed the patients are informed about the trial and the informed consent process is initiated (it is very important that the patient take time to address any question or doubt with the study physician in line with local law). All study specific information is also found in the informed consent form and will be presented to the patient. The informed consent is a voluntary agreement to participate in research. It is not merely a form that is signed but is

a key process for potential study participants, in which the subject has an understanding of the clinical trial and its risk. In case of a consent, the screening activity proceeds, meaning the inclusion and exclusion criteria as well as the concomitant medication and the medical history are evaluated (Section 5.1 and 5.2).

The investigator or designee must ensure that only patients who meet all the following inclusion and none of the exclusion criteria are offered treatment in the study.

5.1 Inclusion criteria

Patients eligible for inclusion in this study must meet **all** of the following criteria:

- 1. Signed informed consent must be obtained prior to participation in the study.
- 2. Men and women ≥ 18 years of age
- 3. Newly diagnosed with primary ITP (time from diagnosis within 3 months) Platelet count $< 30 \times 10^{9}$ /L at screening and a need for treatment (per physician's discretion) Note: If pre-treatment is necessary, platelet count data performed directly before pre-treatment (prior to signing the study specific informed consent form and start of screening for the study as per local practice or under a local protocol) can be used for study inclusion (screening value). Treatment-naïve patients will be included based on their platelet counts performed at screening.

5.2 Exclusion criteria

Patients meeting any of the following criteria are not eligible for inclusion in this study.

- 1. Previous history of treatment for ITP
 - Note: Patients in need of immediate treatment for thrombocytopenia while diagnosis or eligibility are being determined may receive treatment with any ITP-directed therapy for a maximum of 3 days within 7 days before randomization. These therapies must be discontinued before the patient receives the first dose of study treatment
- 2. Patients with diagnosis of secondary thrombocytopenia
- 3. Patients who have life threatening bleeding complications per physician's discretion
- 4. Patients with a history of thromboembolic events in the 6 months preceding enrollment or known risk factors for thromboembolism (e.g. Factor V Leiden, ATIII deficiency, antiphospholipid syndrome) are excluded. Patients with other risk factors which may pose an increased thromboembolic event (TEE) risk (prolonged periods of immobilization, malignancies, contraceptives and hormone replacement therapy, surgery/trauma, obesity and smoking) would be excluded according to the discretion of the investigator.
- 5. Presence of moderate to severe impaired renal function as indicated by any or all of the following criteria:
 - Creatinine clearance < 45 mL/min as calculated using Cockcroft-Gault formula
 - Serum creatinine > 1.5 mg/dL
- 6. Total bilirubin (TBIL) $> 1.5 \times$ upper limit of normal (ULN)
- 7. Aspartate transaminase (AST) $> 3.0 \times ULN$
- 8. Alanine transaminase (ALT) $> 3.0 \times ULN$

9. Patients who are human immunodeficiency virus (HIV), HCV or hepatitis B surface antigen (HBsAg) positive

Confidential

- 10. Patients with hepatic impairment (Child-Pugh score > 5)
- 11. Patients with known active or uncontrolled infections not responding to appropriate therapy
- 12. History of current diagnosis of cardiac disease or impaired cardiac function denoted by any of the following:
 - Corrected QTc >450 msec using Fridericia correction (QTcF) on the screening electrocardiogram (ECG)
 - History of myocardial infarction and unstable angina within 6 months prior to starting study treatment
 - Clinically significant cardiac arrhythmias or other clinically significant cardiovascular disease (e.g., congestive heart failure, uncontrolled hypertension) within the six months prior to starting study treatment
- 13. Patients who have active malignancy
- 14. Patients with evidence of current alcohol/drug abuse
- 15. Any serious and/or unstable pre-existing medical (including any advanced malignancy other than the disease under study), psychiatric disorder, or other conditions that could interfere with subject's safety, obtaining informed consent or compliance with the study procedures.
- 16. Patients with a known immediate or delayed hypersensitivity reaction or idiosyncrasy to eltrombopag or drugs chemically related to eltrombopag or excipients that contraindicate their participation
- 17. Patients with pre-existing medical conditions that are known precautions with corticosteroid use, in whom the potential risks of participating in the study outweigh the potential benefits as determined by the investigator
- 18. Female subjects who are nursing or pregnant (positive serum or urine B-human chorionic gonadotrophin (B-hCG) pregnancy test) at screening or pre-dose on Day 1
- 19. Women of child-bearing potential, defined as all women physiologically capable of becoming pregnant, unless they are using highly effective methods of contraception while taking study treatment and for 7 days after stopping medication. Highly effective contraception methods include:
 - combined (estrogen and progestogen containing) hormonal contraception associated with inhibition of ovulation¹:
 - oral
 - intravaginal
 - transdermal
 - progestogen-only hormonal contraception associated with inhibition of ovulation1:
 - oral
 - injectable
 - implantable²
 - intrauterine device (IUD)²
 - intrauterine hormone-releasing system (IUS)²

- bilateral tubal occlusion²
- vasectomised partner^{2,3}
- sexual abstinence⁴

¹Hormonal contraception may be susceptible to interaction with the IMP, which may reduce the efficacy of the contraception method (see section 4.3).

² Contraception methods that in the context of this guidance are considered to have low user dependency. ³ Vasectomised partner is a highly effective birth control method provided that partner is the sole sexual partner of the WOCBP trial participant and that the vasectomised partner has received medical assessment of the surgical success.

⁴ In the context of this guidance sexual abstinence is considered a highly effective method only if defined as refraining from heterosexual intercourse during the entire period of risk associated with the study treatments. The reliability of sexual abstinence needs to be evaluated in relation to the duration of the clinical trial and the preferred and usual lifestyle of the subject.

6 Treatment

6.1 Study treatment

Patients randomized to Arm A will receive eltrombopag in combination with a short course of high-dose dexamethasone beginning at Day 1. The dose of dexamethasone will be 40 mg QD for 4 consecutive days and limited to 1 cycle. The starting dose of eltrombopag will be 50 mg QD and treatment will continue at the same dose for 2 weeks to reach a target platelet count of 50×10^{9} /L as necessary to reduce the risk for bleeding. The dose of eltrombopag will be increased by 25 mg increments every 2 weeks to a maximum dose of 75 mg QD for all patients who do not achieve the target platelet count of $> 50 \times 10^{9}$ /L (Table 6-1). Treatment with eltrombopag will be continued at the minimal dosage necessary to maintain a platelet count \geq 50 × 10⁹/L to 150 × 10⁹/L for 20 weeks. Asian patients will initially receive half of the dose, starting at 25 mg of eltrombopag due to lower clearance of eltrombopag as compared with non-asian patients. After initiating eltrombopag, the dose must be adjusted to achieve and maintain a platelet count $> 50 \times 10^9$ /L as necessary to reduce the risk for bleeding. The standard eltrombopag dose adjustment for Asian patients would be 25 mg once daily as well. It is necessary to wait for at least 2 weeks to see the effect of any dose adjustment on the patient's platelet response prior to considering another dose adjustment. A daily dose of 75 mg must not be exceeded. The dose of eltrombopag will be decreased by 25 mg if platelet counts are $> 150 \times 10^{9}$ /L to $\leq 400 \times 10^{9}$ /L by 25 mg and the effect will be assessed after 2 weeks.

Patients will be eligible for taper off and treatment discontinuation once they reach platelet counts $\ge 30 \times 10^9$ /L. The duration of tapering will be 6 weeks starting at W21D1: decrease in dose will be performed by 25 mg reductions every 2 weeks to a minimum dose of 25 mg every other day for all patients.

Table 6-1Eltrombopag dosing guidance for patients not meeting criteria for
sustained response

Platelet Level	Dose Guidance	
Patients with platelet < 30×10 ⁹ /L after 4 weeks of eltrombopag therapy at 75 mg/day	Discontinue eltrombopag, initiate second-line therapy, follow-up till week 52 and discontinue from study at Week 52	
Patients who relapse (platelet count < 30×10 ⁹ /L) during eltrombopag tapering off stage	Use previous dose level (i.e. one dose level higher) and continue treatment till Week 52 and discontinue from study at Week 52	
Patients who relapse (< 30×10 ⁹ /L) after eltrombopag discontinuation before Week 52	Re-initiate treatment with eltrombopag with a starting dose of 50 mg/day till Week 52 and discontinue from study at Week 52	

Treatment in the control arm consists of 1-3 cycles of high-dose dexamethasone administered orally at a dose of 40 mg QD for 4 consecutive days at 4 weeks intervals (dexamethasone can also be given at 14 to 28 days intervals if needed according to current ITP guidelines). If the platelet counts are $> 150 \times 10^{9}$ /L no further course of dexamethasone will be given. Patients will be treated up to 12 weeks (3 months) during the treatment period with dexamethasone. Patients who reach platelet counts $\ge 30 \times 10^{9}$ /L and maintain counts $\ge 30 \times 10^{9}$ /L after 1-3 cycles of high-dose dexamethasone treatment will be eligible for treatment discontinuation. Patients with platelet counts $< 30 \times 10^{9}$ /L after 3 cycles of dexamethasone treatment will be offered a course of eltrombopag treatment within the study and will discontinue the study after completion of treatment with eltrombopag at Week 52 (Table 6-2).

Table 6-2Dexamethasone dosing guidance for patients not meeting criteria for
sustained remission

Platelet Level	Dose Guidance
Patients with platelet count < 30×10 ⁹ /L after 3 cycles with dexamethasone	Initiate treatment with eltrombopag with a starting dose of 50 mg/day and continue treatment with eltrombopag till Week 52 after study start and discontinue from study at Week 52
Patients who relapse (platelet count < 30×10 ⁹ /L) after dexamethasone discontinuation before Week 52	Initiate treatment with eltrombopag with a starting dose of 50 mg/day till Week 52 after study start and discontinue from study at Week 52

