- Screening Period: Patients will be screened based on the inclusion and exclusion criteria specified in Section 5.1 and Section 5.2, respectively.
- Treatment Period:

Arm A: Patients will be treated for 26 weeks (6 months) during the treatment period. Patients who reach platelet counts $\geq 30 \times 10^{9}/L$ and maintain counts $\geq 30 \times 10^{9}/L$ during the tapering phase will be eligible for treatment discontinuation. Duration of tapering before treatment discontinuation at Week 26 will be 6 weeks.

Arm B. Patients will be treated up to 12 weeks (3 months) during the treatment period. Patients who reach platelet counts $\geq 30 \times 10^9$ /L and maintain counts $\geq 30 \times 10^9$ /L after 1-3 cycles of dexamethasone treatment will be eligible for treatment discontinuation. Patients with platelet counts $< 30 \times 10^9$ /L after 3 cycles of dexamethasone treatment will be offered a course of eltrombopag treatment within the study and will discontinue from study at Week 52.

• Observation period: After completion of treatment period, patients will be observed for sustained response off treatment.

Arm A: Patients who successfully taper off, discontinue eltrombopag and maintain platelet counts $\geq 30 \times 10^{9}$ /L in the absence of bleeding or use of any rescue therapy will be observed until Week 52 after study start. Patients who relapse after eltrombopag discontinuation will reinitiate treatment with eltrombopag till Week 52 and will discontinue from study at Week 52. Patients with platelet counts $< 30 \times 10^{9}$ /L after 26 weeks of treatment with eltrombopag will continue eltrombopag treatment till Week 52 and discontinue from study at Week 52.

Arm B: Patients who successfully discontinue dexamethasone treatment and maintain platelet counts $\geq 30 \times 10^{9}$ /L in the absence of bleeding or use of any rescue therapy will be observed until Week 52 after study start. Patients who relapse (platelet count < 30 × 10⁹/L) after dexamethasone discontinuation and need treatment will be treated with eltrombopag until Week 52 after study start and discontinue from study at Week 52. Patients with platelet count < 30 × 10⁹/L after 3 cycles with dexamethasone will initiate treatment with eltrombopag and discontinue the study at Week 52.

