6.1.4 Treatment duration

Arm A: The treatment duration for all patients in Arm A (eltrombopag QD for 26 weeks + high-dose dexamethasone QD for 4 consecutive days starting at day 1 and limited to 1 cycle) will be 26 weeks (6 months) including 6 weeks tapering period. All patients who discontinue study treatment as per study design with platelet counts $\geq 30 \times 10^{9}$ /L in the absence of bleeding or use of any rescue therapy will be followed for response assessments till Week 52 after study start. Patients who relapse after eltrombopag discontinuation before Week 52 will reinitiate treatment with eltrombopag till Week 52 and will discontinue from study at Week 52. Patients with platelet counts < 30×10^{9} /L after 26 weeks of treatment with eltrombopag will continue treatment as summarized in Table 6-1 and discontinue from study at Week 52.

Arm B: The maximum duration of treatment with dexamethasone for all patients in Arm B will be 12 weeks. All patients who discontinue study treatment as per study design with platelet counts $\geq 30 \times 10^9/L$ in the absence of bleeding or use of any rescue therapy will be followed for response assessments till Week 52. Patients who relapse (platelet count $< 30 \times 10^9/L$) after dexamethasone discontinuation before Week 52 will be treated with eltrombopag as summarized in Table 6-2 and discontinue the study at Week 52. Patients with platelet count $< 30 \times 10^9/L$ after 3 cycles with dexamethasone will initiate treatment with eltrombopag and discontinue the study at Week 52.

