6.5 Dose escalation and dose modification

6.5.1 Dose escalation guidelines

Dose escalation will be allowed from 50 mg QD to 75 mg QD for eltrombopag as described in Section 6.1. Patients will be treated with eltrombopag 50 mg QD for 2 weeks to reach a target platelet count of \geq 50 × 10⁹/L. For those patients who do not achieve the target platelet count within 2 weeks, the dose of eltrombopag will be increased to 75 mg QD.

Patients who will have platelet $< 30 \times 10^{9}$ /L after 3 cycles with dexamethasone, treatment with eltrombopag will be initiated at 50 mg/day till Week 52 with eltrombopag dose adjustments summarized in Table 6-4.

All escalations and de-escalations must be recorded on the Dosage Administration Record eCRF.

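### For an Arm A patient still below 30 × 10⁹/L at Week 26 after at least 4 weeks at 75 mg/day, Table 6-1 stops eltrombopag and Section 3 continues it; whether the stop applies after re-initiation or the Arm B switch is not stated

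*Protocol*

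**What the plan says.** Protocol Section 6.1, Table 6-1, has three rows.

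- **Row 1** is for platelets below 30 × 10⁹/L "after 4 weeks of eltrombopag therapy at 75 mg/day". The action is "Discontinue eltrombopag, initiate second-line therapy, follow-up till week 52 and discontinue from study at Week 52". The row names no arm and no calendar window.
- **Row 2** is for relapse during the taper: "Use previous dose level (i.e. one dose level higher) and continue treatment till Week 52 and discontinue from study at Week 52".
- **Row 3** is for relapse after eltrombopag has been discontinued. It restarts the drug and runs it to Week 52.

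Section 3 (observation period, Arm A) says that patients below 30 × 10⁹/L "after 26 weeks of treatment with eltrombopag will continue eltrombopag treatment till Week 52 and discontinue from study at Week 52". Section 6.1.4 covers the same patients but words it differently: they "after 26 weeks of treatment with eltrombopag will continue treatment as summarized in Table 6-1". Both sections also give 26 weeks as the Arm A treatment duration and make no exception for row 1.

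For Arm B patients below 30 × 10⁹/L after three dexamethasone cycles, Table 6-2 says "Initiate treatment with eltrombopag with a starting dose of 50 mg/day and continue treatment with eltrombopag till Week 52 after study start". Its second row does the same for relapse after dexamethasone. Section 6.5.1 takes the three-cycle failures "till Week 52 with eltrombopag dose adjustments summarized in Table 6-4" and does not cite Table 6-1.

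**The concern.** A dosing protocol should give one instruction for one clinical state. Here a patient below 30 × 10⁹/L after an adequate period at the top dose is told in one place to stop and move to second-line therapy, and in another to stay on the drug. The cross-reference that might settle the matter leads to a table without a matching row. The protocol itself links counts below 20–30 × 10⁹/L to the greatest bleeding risk (Section 1.1.2), so these patients' treatment should not depend on which section a site opens first.

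The statistical stake is smaller. Where sites resolve the texts differently, late-study summaries mix two management paths. If the stop is applied in Arm A but not after the Arm B switch, that mix could differ by arm.

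**Working it through.** No stated figure has to be reproduced. The check is a timeline from the protocol's own dose steps, followed by a comparison of the texts for each type of patient. In visit labels, n elapsed weeks is Week n+1 Day 1.

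**Timeline**

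- Standard start (6.5.1): 50 mg for 2 weeks, then 75 mg. Earliest row 1 date = 2 + 4 = 6 elapsed weeks (W7D1).
- 25 mg start (6.1), two steps of 2 weeks: 75 mg at week 4. Earliest row 1 date = 4 + 4 = 8 elapsed weeks (W9D1).
- Taper (6.1): 6 weeks from W21D1, ending at Week 26.
- Latest start of 75 mg that gives 4 full weeks by Week 26: 26 − 4 = Week 22.
- Longest span of a conflict that begins at Week 26: 52 − 26 = 26 weeks.

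**Texts side by side, by patient (all below 30 × 10⁹/L)**

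| Patient | Table 6-1 | Other text | Result |
|---|---|---|---|
| Arm A, 6–8 weeks, 4 weeks at 75 mg | Row 1: stop | Sections 3 and 6.1.4 give 26 weeks of treatment with no exception | Loose wording; Section 3's Week 26 rule not yet reached |
| Arm A, relapse in taper | Row 2: continue | Section 3: continue | Agree |
| Arm A, untapered at Week 26, at least 4 weeks at 75 mg | Row 1: stop | Section 3: continue; 6.1.4: continue per Table 6-1 | Opposite instructions, no precedence |
| Arm A, restarted after relapse, then 4 weeks at 75 mg | Row 3: treat to Week 52; row 1: stop | No further text | Unclear |
| Arm B after the switch, then 4 weeks at 75 mg | Row 1 names no arm | Table 6-2: to Week 52; 6.5.1 cites only Table 6-4 | Unclear |

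Section 6.1.4 cannot be followed for the third patient. Table 6-1 continues only taper relapsers (row 2) and re-initiated patients (row 3), and the row that fits says stop. Table 6-4 does not fill the Arm B gap: its actions are a dose increase, a decrease, and a stop that restarts once the count is below 150 × 10⁹/L. None is a stop for lack of response.

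**Effect on the analyses for the third patient**

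- *Primary endpoint.* If eltrombopag continues to Week 52, the patient is never off treatment. If it stops and second-line therapy starts, Section 6.2.3 makes the patient a non-responder. Same status either way.
- *Platelet-only sensitivity analysis (SAP 2.5.4).* In Arm A it needs counts of at least 30 × 10⁹/L from the start of tapering at week 20 to Week 53. A patient below 30 × 10⁹/L at Week 26 has already failed it.
- *On-treatment exposure and adverse-event window.* SAP 2.1.1 defines Arm A study treatment as eltrombopag until Week 26 and leaves additional dosing to case-by-case review. Most of the disputed dosing therefore falls outside.
- *What can move.* Week 52 platelet counts and quality of life, mean dose after Week 27 (SAP 2.4.1), and rescue counts (SAP 2.4.2). At about 12 patients per arm, one patient is 1/12, or about 8 percentage points, of a descriptive rate.

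**The case against.** The strongest reply is that the rules apply in sequence. A patient who never responds meets row 1 at 6 to 8 weeks, is stopped, and never accumulates the 26 weeks of treatment that Section 3 requires. Those still treated and below 30 × 10⁹/L at Week 26 would then mostly be taper relapsers, for whom row 2 and Section 3 agree. Section 6.1.4 defers to Table 6-1 rather than opposing it. Table 6-2 is defined by dexamethasone failure or relapse and says nothing on later eltrombopag failure.

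Much of this stands, and it rules out three stronger readings.

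- A reader might count the conflict from W7D1 to Week 52 (52 − 7 = 45 weeks). That joins row 1 to a Section 3 rule with a different entry condition. No text tells a site to carry the Week 7 patient through to Week 52.
- A reader might say that Table 6-2 orders continued eltrombopag in patients who have failed it, and attach a fixed duration. The table neither applies nor disapplies row 1, so this is a gap. Its second row also allows a start at any time up to Week 52, so no fixed range follows.
- A reader might expect the primary result or the platelet-only analysis to shift. In the direct conflict neither can.

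The reply does not remove the overlap. It assumes that row 1 takes precedence, which no text states. Section 3 is written without exception, and an untapered patient who began 75 mg by about Week 22 can meet both conditions at Week 26.

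**Conclusion.** The contradiction is real but narrow. It concerns an Arm A patient who is untapered, on eltrombopag at Week 26, below 30 × 10⁹/L, and has had at least 4 weeks at 75 mg/day. Table 6-1 and Section 3 give that patient opposite instructions for up to 26 weeks, and the Section 6.1.4 reference has no row to land on. Beside it are two gaps: whether row 1 applies after re-initiation under row 3, and whether it applies after the Arm B switch.

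This rests on reading row 1 as at least 4 weeks at 75 mg/day and on escalation at the stated 2-week steps. The documents do not allow a count of affected patients. With about 24 enrolled and a purely descriptive analysis, it may be few or none. The consequences are inconsistent management of patients below 30 × 10⁹/L and some late descriptive outputs; primary-endpoint status is unaffected.

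**What to change.** Reconcile Section 3 (Arm A treatment and observation periods), Section 6.1.4, Table 6-1, Table 6-2 and Section 6.5.1, so that one rule, with its precedence stated, covers a patient below 30 × 10⁹/L after 4 weeks at 75 mg/day. In doing so:

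- correct the 6.1.4 cross-reference so that it leads to a row fitting an untapered patient at Week 26;
- say whether the 26-week Arm A duration is subject to row 1;
- say whether row 1 applies after re-initiation and after the Arm B switch.

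Which rule applies is for the sponsor and steering committee to decide. The cost is wording in five places and a site letter, with no extra visits or patients. If treatment has already ended, the equivalent step is a listing in the study report of any patient who met the row 1 condition and the course followed.
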